Confidential

	In order to calculate the sample size for the study, initially a requirement was chosen that the length of the 95% confidence interval of the mean change from baseline to 4h does not exceed 0.2 mmol/L at an observed historical standard deviation of 0.3. With a targeted minimum of 25 subjects evaluable for this endpoint, the length of this confidence interval is maintained with a slight increase to 0.25 mmol/L. The safety data analysis will be presented with special focus on LysaKare [®] related treatment emergent events and will be applied to the full Safety Set. Changes in Vital Signs and ECG will be summarized by time. Changes in laboratory parameters (Haematology and Blood Chemistry) will be described by time.
Key words	LysaKare [®] , amino acid, GEP-NET, PRRT, Lutathera [®]

Advanced Accelerator Applications Clinical Trial Protocol (Version 01)

Confidential

Version history

Version Number	Description
Global protocol v00 dated 12-Nov-2019	Initial global protocol. Approved in all countries.
Local protocol v00 PL.01 dated 18-May-2021	Local amended protocol from v00. Approved in Poland
Global protocol v01 dated 01-Dec-2022	Amended global protocol from v00 and local protocol v00-PL.01 dated 18-May-2021

Protocol Amendment 01

As of 08 November 2022, 30 patients were enrolled into the study and received an infusion of LysaKare[®].

Amendment rationale

The primary purpose of this amendment is to provide clarification on the sampling requirements for laboratory assessments. The Sponsor identified discrepancies in sampling used for electrolytes which were not performed as per protocol requested procedures. This resulted in samples collected with heparinized blood (2 patients) and whole blood (11 patients) instead of serum sampling across 4 sites. Therefore, the Visit Schedule and assessments in Section 8 have been updated to clarify the requirements of laboratory assessments.

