12.8 Sample size calculation

The primary endpoint is the change in serum potassium levels after LysaKare[®] IV administration compared to baseline. In a previous study, which assessed hourly potassium

Advanced Accelerator Applications Clinical Trial Protocol (Version 01)

Confidential

changes in 11 patients treated with LysaKare[®], peak concentration was observed at 2-4 h postbaseline, the mean baseline level was 4.2 mmol/L, mean increase at 2 h was 0.6 mmol/L and at 4 h it was 0.9 mmol/L (SD=0.3); the maximum increase was 1.5 mmol/L (Krenning 2000). The mild increase in potassium levels did not manifest in any safety issues or clinically significant events. Since the maximum mean increase was observed at 4h, the change from baseline to 4h will be of primary interest.

The current study will describe the expected mean change at 4h by a point estimate and the corresponding 95% confidence interval. In historical data a mean increase from baseline to 4h of 0.9 mmol/L was observed with a standard deviation of 0.3.

The criterion for choice of sample size will be based on length of confidence interval of the mean change at 4h calculated using the t-distribution. A requirement was initially chosen that the confidence interval has a total length not exceeding 0.2 mmol/L assuming the historical standard deviation to be valid, i.e. the distance should be no more than 0.1 mmol/L from the mean to the limit of the confidence interval when the estimated standard deviation is 0.3.

The initially estimated sample size of 38 subjects produces a two-sided 95% confidence interval with a distance from the mean to the limits that is equal to 0.099 when the estimated standard deviation is 0.3. With the required minimum number of 25 evaluable subjects for the primary endpoint analysis, the confidence interval (CI) total length is maintained with a slight increase to 0.25 mmol/L. Additionally, the originally estimated sample size of 38 implies an adequate probability of observing common AEs, see Table 12-1 below. This estimate holds true because the current laboratory sampling issue only impacts the evaluable number for the primary endpoint. Other safety assessments based on AEs remain evaluable for the whole safety set.

Sample size	Incidence of Adverse Event	
	5%	10%
10	0.401	0.651
20	0.642	0.878
30	0.785	0.958
38	0.858	0.982
40	0.871	0.985

Table 12-1 Likelihood of observing at least one case for given
sample size and incidence

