The table displays the probability of observing at least one case of a certain AE which has the incidence 5% or 10% in this patient population for the sample sizes 10, 20, 30 and 40. Any further increase in total sample size ensures that this probability remains above 87%.

Since the sample size of 38 subjects assumes no drop-out, additional subjects have been added to hedge against drop-out. Given the design of the study, no or very minor drop-out is expected. The additional precaution is taken to ensure at least 25 subjects are evaluable for the primary endpoint analysis as discussed in the amendment rationale. Therefore, the adjusted sample size is approximately 45 subjects.

13 Ethical considerations and administrative procedures

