2.7.1.1 Adverse events of special interest (AESI)

Hyperkalemia is the only AESI. The search strategy will be MedDRA PTs Hyperkalaemia and Blood potassium increased.

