2.7.3 Laboratory data

On analyzing laboratory data, data from all sources will be combined. The summaries will include all assessments available for the lab parameters collected no later than 24 hours after the start of the LysaKare[®] infusion. The laboratory parameters that will be investigated, and the timing that the laboratory parameters will be assessed are summarized in Table 2-1.

	ematology and Chemist		incitta
Haematology (Assessment at screening, pre-dose and 24h after start of the infusion)	Blood Chemistry (serum) (Assessment at screening, pre-dose and 24h after start of the infusion)	Electrolytes (serum) (Assessment at screening, pre-dose and 2h, 4h, 6h, 8h, 12h and 24h after start of the infusion)	Venous Blood Gas (Assessment at screening, pre-dose and 2h, 4h, 6h, 8h, 12h and 24h after start of the infusion)
WBC with differential	BUN or urea	Potassium	рН
Platelets	Uric acid	Sodium	Lactate
Haemoglobin	Serum creatinine	Chloride	pCO2
Haematocrit	Creatinine clearance* Albumin Total bilirubin Alkaline phosphatases AST/ASAT ALT/ALAT	HCO3	
	Gamma-GT		
	Glucose		
	LDH		

Table 2-1 Hematology and Chemistry Laboratory Assessments

(*) Calculated using Cockcroft-Gault formula

Laboratory values outside normal ranges will be listed and flagged. The following flags will be used:

'+': 'Higher than reference value'

'-': 'Lower than reference value'

The respective parameter and the flagged value will be presented patient-wise by visit together with the reference values.

Advanced Accelerator Applications,	Confidential	Page 19 of 27
A Novartis company		
SAP amendment		CAAA001A12401

The following summaries will be produced for hematology and biochemistry laboratory data (by laboratory parameter and treatment):

- Worst post-baseline Common Toxicity Criteria (CTC) grade (regardless of the baseline status). Each subject will be counted only for the worst grade observed post-baseline.
- Shift tables using CTC grades to compare baseline to the worst on-treatment value.
- For laboratory tests where CTC grades are not defined, shift tables using the low/normal/high/(low and high) classification to compare baseline to the worst on-treatment value.

The following listings will be produced for the laboratory data:

- Listings of all laboratory data, with CTC grades and classification relative to the laboratory normal range. Lab data collected during the post-treatment period will be flagged.
- Listing of all CTC grade 3 or 4 laboratory toxicities.

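### The claim that the sampling error touches only the primary endpoint is too broad: non-serum potassium can also feed the hyperkalaemia rate and the potassium grade tables

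*Protocol*

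**What the plan says.** The Amendment 01 rationale in the protocol reports the error: "The Sponsor identified discrepancies in sampling used for electrolytes which were not performed as per protocol requested procedures". Two patients had heparinized samples and 11 had whole-blood samples, at 4 sites, out of 30 enrolled by 08 November 2022. The rationale bars these potassium values from the primary endpoint but keeps the patients' other data, including adverse events, for the safety objective.

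Protocol 12.8 then states that "the originally estimated sample size of 38 implies an adequate probability of observing common AEs", and defends this with "This estimate holds true because the current laboratory sampling issue only impacts the evaluable number for the primary endpoint". It adds: "Other safety assessments based on AEs remain evaluable for the whole safety set". SAP 3 repeats the argument.

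Elsewhere the SAP makes these provisions:

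- 2.7.1.1: "Hyperkalemia is the only AESI". It is found by two MedDRA preferred terms, one of which is a purely laboratory term for raised blood potassium.
- 2.7: all safety analyses use the Safety Set.
- 5.4.2: the percentage with hyperkalaemia is reported with a Clopper-Pearson 95% interval.
- 2.5.6: whole-blood potassium may be overestimated. The same section tabulates potassium by normal range and CTC grade over the Safety Set at each time point, whatever the sample type.

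**The concern.** The sentence in 12.8 treats adverse events as independent of the faulty samples. That is reasonable for nausea or vomiting. It is not reasonable for hyperkalaemia, where a potassium value is often what prompts the report. Protocol 10.1.1 lets an abnormal laboratory value count as an adverse event if it is judged clinically significant, without symptoms. Protocol 8.4.2 sends any clinically relevant laboratory change to the adverse-event page.

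The values kept out of the mean-change analysis can therefore return through two other routes: the hyperkalaemia rate and the grade table. Neither is split by specimen. In a descriptive safety study about potassium, a reader would take both as estimates of how often LysaKare raises potassium to a notable level. An upward measurement error in part of the sample would be read as a drug effect.

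**Working it through.** **1. The plan's own table.** Protocol Table 12-1 and SAP Table 3-1 give the chance of at least one case, P = 1 − (1 − p)^n.

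- n = 38, p = 5%: 1 − 0.95^38 = 0.8576 (stated 0.858).
- n = 38, p = 10%: 1 − 0.90^38 = 0.9818 (stated 0.982).
- The other eight cells also reproduce.
- At the planned total of about 45: 1 − 0.95^45 = 0.901 and 1 − 0.90^45 = 0.991.

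The table is correct. It describes a generic event of 5% or 10% incidence, and neither document gives an incidence for hyperkalaemia.

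**2. Where the faulty samples go.** The error was in electrolyte sampling (Amendment 01 rationale), and potassium is in that panel (Protocol Table 8-2).

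| Output | Set | Sample-type rule |
|---|---|---|
| Change in serum potassium (SAP 2.5.1) | Evaluable Set | Serum potassium required |
| Hyperkalaemia rate, exact interval (SAP 2.7.1.1, 5.4.2) | Safety Set | None |
| Potassium normal-range and CTC categories (SAP 2.5.6) | Safety Set | Pooled by design |

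Only the first row is protected. The word 'only' fails on the other two.

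**3. Share affected.** 2 + 11 = 13 patients. 13/30 = 43% of those enrolled at the time. If no further errors occur and 45 are treated, 13/45 = 29%, leaving 45 − 13 = 32 with correct samples.

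**4. Direction and size.** Let e be the added false-positive risk in the 13 patients. The documents give no value, so 2, 5 and 10 percentage points are assumed. With p = 5%:

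- P(at least one recorded case) = 1 − 0.95^32 × (0.95 − e)^13
- Expected recorded rate = 5% + (13/45) × e

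| e | P(at least one) | Expected recorded rate |
|---|---|---|
| 0 | 0.901 | 5.0% |
| 2 points | 0.925 | 5.6% |
| 5 points | 0.951 | 6.4% |
| 10 points | 0.977 | 7.9% |

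The chance of recording a case goes up. What suffers is the meaning of the rate.

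**5. Effect on the reported interval (assumed counts).** The Clopper-Pearson limits are the 2.5% point of Beta(x, n − x + 1) and the 97.5% point of Beta(x + 1, n − x).

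- Two true cases in 45: 4.4% (0.5 to 15.1%).
- The same two plus two false cases: 4/45 = 8.9% (2.5 to 21.2%).
- The same four cases split, with the true ones in serum patients and the false ones in the rest: 2/32 = 6.25% (0.8 to 20.8%) and 2/13 = 15.4% (1.9 to 45.4%).

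The pooled figure hides what the split would show.

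**The case against.** Four things can be said in favour of the plan.

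First, Table 12-1 is generic and right, and the text around it speaks of common adverse events in general. This stands. A reader might infer that the detection probability for hyperkalaemia falls to the value for 25 patients, 1 − 0.95^25 = 0.723 at 5% incidence, or for 32 patients, 1 − 0.95^32 = 0.806. The documents do not support that. No rule confines hyperkalaemia to serum-measured patients, the 13 were dosed, tested and observed, and the one error direction on record is upward.

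Second, a hyperkalaemia event is more than a reading. Protocol 10.1.1 requires symptoms, clinical significance, therapy or a change in study medication. This limits the contamination but does not remove it, because clinical significance can be judged from the value alone.

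Third, SAP 2.5.6 already states the overestimation caveat, runs an all-source analysis of change, and excludes patients with a whole-blood baseline from it. Pooling the grade table can also be defended as cautious, since it errs towards showing more hyperkalaemia. Both are fair, but the exclusion does not reach the grade table or the event rate, and a cautious figure is still a biased estimate if shown alone.

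Fourth, sodium, chloride and HCO3 come from the same panel, so a reader might want a serum-only rule for them too. The documents record no specimen bias for these three. SAP 2.5.6 analyses them by repeating the primary analysis, which runs on the serum-potassium Evaluable Set. The line in SAP 2.7.3, "On analyzing laboratory data, data from all sources will be combined", does not clearly refer to specimen type, and nothing here rests on it.

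**Conclusion.** The statement that the sampling issue affects only the primary endpoint is too broad. Non-serum potassium from up to 13 of about 45 patients (29%) can also enter the hyperkalaemia rate and the elevated-potassium frequencies, and may inflate both. The detection probabilities are correct and are not lowered.

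This is a modest point about how two safety outputs can be interpreted, not an arithmetic error. It rests on three assumptions: that the 13 patients lack serum potassium at the relevant times, that no further sampling errors occur, and that the whole-blood bias is upward, as the SAP says it may be. The documents give no direction for the two heparinized patients and no size for the bias, so the inflation can be illustrated but not estimated.

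**What to change.** 1. In Protocol 12.8 and SAP 3, reword the sentence to say that adverse events not based on potassium values are unaffected by the sampling issue, while potassium-based events may be affected. Leave Tables 12-1 and 3-1 as they are.
2. In SAP 2.5.6 and 5.4.2, present the potassium normal-range and CTC-grade frequencies, and the hyperkalaemia rate with its exact interval, separately for patients with serum and with non-serum potassium, beside the pooled Safety Set figure. Add one line on how to classify a patient who has both.

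This costs a sentence in each document and a split of existing tables. It needs no new data, provided that specimen type is recorded, which the Evaluable Set definition already requires for potassium. The serum-only interval will be wider: with two cases it spans 20.8 − 0.8 = 20.0 points at n = 32, against 15.1 − 0.5 = 14.6 at n = 45.

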13.1 Regulatory and ethical compliance

This clinical study was designed and shall be implemented, executed and reported in accordance with the ICH Harmonized Tripartite Guidelines for Good Clinical Practice, with applicable local regulations (including European Directive 2001/20/EC, US CFR 21), and with the ethical principles laid down in the Declaration of Helsinki.

13.2 Responsibilities of the investigator and IRB/IEC

Before initiating a trial, the investigator/institution must obtain approval/favorable opinion from the Institutional Review Board/Independent Ethics Committee (IRB/IEC) for the trial protocol, written informed consent form, consent form updates, subject recruitment procedures (e.g., advertisements) and any other written information to be provided to subjects. Prior to study start, the investigator is required to sign a protocol signature page confirming his/her agreement to conduct the study in accordance with these documents and all of the instructions and procedures found in this protocol and to give access to all relevant data and records to Advanced Accelerator Applications monitors, auditors, Advanced Accelerator Applications Quality Assurance representatives, designated agents of Advanced Accelerator Applications, IRBs/IECs, and regulatory authorities as required. If an inspection of the clinical site is requested by a regulatory authority, the investigator must inform Advanced Accelerator Applications immediately that this request has been made.

13.3 Publication of study protocol and results

The protocol will be registered in a publicly accessible database such as clinicaltrials.gov and as required in EudraCT. In addition, after study completion (defined as last patient last visit) and finalization of the study report the results of this trial will be submitted for publication and posted in a publicly accessible database of clinical trial results, such as the Advanced Accelerator Applications clinical trial results website and all required Health Authority websites (e.g. Clinicaltrials.gov, EudraCT etc.).

Advanced Accelerator Applications (AAA) follows the ICMJE authorship guidelines (www.icmje.org). Authors (including Sponsor associates who may qualify for authorship), must therefore satisfy all of the following ICMJE authorship criteria:

- 1. Substantial contributions to conception or design of the work; or the acquisition, analysis, or interpretation of data for the work; AND
- 2. Drafting the work or revising it critically for important intellectual content; AND
- 3. Final approval of the version to be published; AND
- 4. Agreement to be accountable for all aspects of the work in ensuring that questions related to the accuracy or integrity of any part of the work are appropriately investigated and resolved.

Advanced Accelerator Applications Clinical Trial Protocol (Version 01)

Confidential

The key principles that will be followed for AAA-sponsored, research-related publications are:

- AAA supports the publication of study results for its innovative medicines in a timely manner, whatever their outcome. AAA policy is not to withhold, veto or suppress data. However, due consideration must be given to the rights of AAA to protect confidential and/or patentable information, and to the protection of personal information, in particular patient privacy.
- Review by AAA of draft publications by clinical investigators in advance of submission/presentation of publication is designed to:
 - Confirm the accuracy of the data
 - Verify that proprietary information is not being inadvertently disclosed
 - Secure intellectual property rights, as needed
 - Provide any relevant supplementary information
- Publication of partial data (unless planned in the protocol) is discouraged. As a matter of scientific rigor and fairness to all investigators involved in a clinical study, and in accordance with the Joint Position on the Publication of Clinical Trial Results in the Scientific Literature, issued by the International Federation of Pharmaceutical Manufacturers and Associations (IFPMA), European Federation of Pharmaceutical Industries and Associations (EFPIA), Japan Pharmaceutical Manufacturers Association (JPMA), and Pharmaceutical Research and Manufacturers of America (PhRMA), it is AAA policy for multicenter clinical studies that:
- The first publication in a journal, or a presentation at a congress, be based on consolidated data from all centers, analyzed as stipulated by the protocol and agreed upon by investigators before trial initiation.
- Multicenter trials are designed to take full account of data accumulated from all centers (sample sized, powered with appropriate error rates), and AAA discourages presenting or publishing data gathered from a single, or small group of centers, unless agreed to by study investigators (e.g., Study Steering Committee) and AAA. Center specific analyses have greater variability and lead to exaggerated observed-treatment effects that are inherently less reliable. Valid conclusions regarding the primary endpoint of a clinical trial can only be based on the analyses predefined by the protocol.
- Study results should be published according to the contracted protocol agreements.

13.4 Quality Control and Quality Assurance

Advanced Accelerator Applications maintains a robust Quality Management System (QMS) that includes all activities involved in quality assurance and quality control, to ensure compliance with written Standard Operating Procedures as well as applicable global/local GCP regulations and ICH Guidelines.

Audits of investigator sites, vendors, and Advanced Accelerator Applications systems are performed by auditors, independent from those involved in conducting, monitoring or

Advanced Accelerator Applications Clinical Trial Protocol (Version 01)

Confidential

Page | 50 Protocol No.CAAA001A12401

performing quality control of the clinical trial. The clinical audit process uses a knowledge/risk based approach.

Audits are conducted to assess GCP compliance with global and local regulatory requirements, protocols and internal SOPs, and are performed according to written Advanced Accelerator Applications processes.

Advanced Accelerator Applications Clinical Trial Protocol (Version 01)

Confidential

Page | 51 Protocol No.CAAA001A12401

14 **Protocol adherence**

This protocol defines the study objectives, the study procedures and the data to be collected on study participants. Additional assessments required to ensure safety of subjects should be administered as deemed necessary on a case-by-case basis. Under no circumstances including incidental collection is an investigator allowed to collect additional data or conduct any additional procedures for any purpose involving any investigational drugs under the protocol, other than the purpose of the study. If despite this interdiction prohibition, data, information, observation would be incidentally collected, the investigator shall immediately disclose it to Advanced Accelerator Applications and not use it for any purpose other than the study, except for the appropriate monitoring on study participants.

Investigators agree to apply due diligence to avoid protocol deviations. If an investigator feels a protocol deviation would improve the conduct of the study this must be considered a protocol amendment, and unless such an amendment is agreed upon by Advanced Accelerator Applications and approved by the IRB/IEC and health authorities, where required, it cannot be implemented.

MedDRA	Medical Dictionary for Regulatory Activities
MMRM	Mixed Model Repeated Measures
mL	Milliliter
NCI	National Cancer Institute
PASS	Post Authorization Safety Study
pCO2	Partial Pressure of Carbon Dioxide
PT	Preferred Term
RAP	Report and Analysis Process
SAE	Serious Adverse Event
SAF	Safety Set
SAP	Statistical Analysis Plan
SD	Standard Deviation
SOC	System Organ Class
SSR	Somatostatin Receptor
TEAE	Treatment Emergent Adverse Event
TFLs	Tables, Figures, Listings
TNM	Tumors, Nodes, Metastases
ULN	Upper Limit of Normal
WBC	White Blood Cells
WHO	World Health Organization
WHO-DRL	World Health Organization-Drug Reference List

Advanced Accelerator Applications,	Confidential	Page 6 of 27
A Novartis company		
SAP amendment		CAAA001A12401

1 Introduction

The purpose of this Statistical Analysis Plan (SAP) is to outline the statistical methods and document the outputs needed for the clinical study report (CSR) of the primary analysis of study CAAA001A12401, a multicenter, open-label, post authorization safety study (PASS) to evaluate the effect of LysaKare[®] infusion on serum potassium levels in Gastroenteropancreatic neuroendocrine tumors (GEP-NET) patients eligible for Lutathera[®] treatment.

The content of this SAP is based on protocol CAAA001A12401 version 01 (release date: 01-Dec-2022). All decisions regarding primary analysis, as defined in the SAP document, have been made prior to database lock of the study data.

